- C. Describe the ability to reproduce potentially important findings from this research in other data sets and populations.** To ensure the generalizability of our results, we selected a large number of practices (30) in several practice networks to get a representative set of practices serving diverse populations. Practices included represent FQHCs as well as nonprofit practice networks serving higher income brackets. Our focus on disparities in CVD care requires that we work in an area with a large number of African-American and Hispanic residents in order to be able to create statistically valid comparisons by race/ethnicity. During the proposal process we went to great lengths to interview, survey, and meet with practice sites with different patient populations, and with representatives of the community and of community support agencies. We convened large groups of clinician researchers and methodologists with patient and community representatives to define the desired intervention and the methods for testing it. We believe this will render the intervention more sustainable in the real world and increase its ability to be reproduced in other settings.

Section 12: Publication Policy

We anticipate submission of at least three manuscripts related to this project, reporting: the methods of the intervention (end year 1), preliminary results (in year 4), and final results (end year 5). However, given the scope of the project, we will most likely complete several additional manuscripts. To promote replication of our intervention elsewhere and to better serve the broader population of hypertensive patients, we will make all informational materials, content, and tools produced as part of this project available to other practice networks and practices. We will also be available to consult for the implementation of this intervention upon request. Overall responsibility for manuscript and abstract generation and approval for the study should be guided by the following authorship principles.

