| Intervention | Few clinical interventions have used collaborative and coordinated care among primary care providers, specialists, nurses, pharmacists, social workers, and other key team members to improve multiple CVD risk factors. | Research is needed to better describe the required level of intervention intensity and detailed descriptions of successful CHW components (e.g., CHW education, training, expertise, supervision, attrition, satisfaction) for effectively improving outcomes. ^{15,74,97,98} | We will measure and document specific components of our collaborative care (CC) intervention (e.g., team dynamics, adherence to guidelines, relationships with patients) and CHW intervention (e.g., CHW personal traits, training) exposure to specialist consultation, that are critical for achieving improved CVD-risk reduction. |
| Comparator | Unknown whether multi-level interventions are more effective than those targeting only patient factors, and which health system QI interventions are most effective. ¹⁵ | Studies are needed to compare the effectiveness of different types of multi-level interventions (with detailed justification for the choice of comparators) across multiple patient populations. ^{15,98} | Our study will compare the effectiveness of enhanced standard of care with a clinic-based multi-level intervention with the added value of a CHW intervention or specialist consultation in reducing CVD risk factors in diverse, high-risk patient groups. |
| Outcome | Little evidence testing whether health system QI interventions are effective at reducing CVD disparities. ¹⁵ Many analyses of study outcomes are limited by small sample sizes. ⁹³ | The evidence base is limited by variations in the specific confounders and effect modifiers that investigators have included or controlled for in their analyses of intervention effectiveness on patient outcomes. ⁹⁸ | We will employ rigorous statistical methods to appropriately control for factors that may influence the observed effect of our CC interventions on reducing disparities in a large population with CVD-risk factors. We are recruiting a large sample with adequate power for subgroup analyses. |

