1. **UH3 Specific Aim 1:** We will conduct a pragmatic clinical trial to test practical, scalable approaches to close the HTN disparities gap. We will compare the effectiveness of a standard of care plus (SCP) intervention (that includes audit/feedback and education) to practice-based collaborative care with a stepped approach (CC/stepped care) that includes community-based contextualized care delivered by a CHW, specialist consultation, or both, to reduce disparities in HTN and improve patient-centered outcomes (self-management behaviors, goal attainment, activation).
2. **UH3 Specific Aim 2:** We will demonstrate patient and stakeholder engagement by applying principles of community-based participatory research (CBPR) to build upon our existing local community board and engage a regional and national stakeholder advisory panel.
3. **UH3 Specific Aim 3:** This study will inform the important question of whether a multi-level intervention that adds a contextualized (i.e., patient and family-centered, community-based) approach to practice-based CC/stepped care will be more effective than SCP alone at improving clinical outcomes and self-management behaviors among patients with hypertension and other common comorbidities and CVD risk factors.

- i. UH3 Hypothesis:** The multi-level intervention with a contextualized (i.e., patient and family-centered, community-based) approach to practice-based CC/Stepped Care will be more effective than SCP in improving clinical outcomes and self-management behaviors among hypertensive patients with other designated conditions.

A. Research design/methodology

1. The design of this study is a prospective cluster-randomized trial of superiority of CC/Stepped Care over SCP. Evidence exists for the effectiveness of both intervention approaches; however, they have not been sustained or translated to practice in real-world settings caring for underserved populations. Further, the proposed comparison has not been done, using a pragmatic approach, to address HTN management to reduce disparities in patient outcomes (see Section 1: Background/Significance).

B. Study population: Inclusion/exclusion criteria

1. Inclusion Criteria:

- a. Practice sites: Thirty primary care clinics in the mid-Atlantic have been enrolled and randomized. Practices must either be Federally Qualified Health Centers (FQHCs) or serve diverse racial and ethnic populations.

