Primary endpoint: The primary endpoint is 12 month follow-up. Analysis on the following outcomes will take place after 12 month follow-up data collection has been completed.

Primary outcomes

The primary clinical outcome of the RICH LIFE Project is the percent of patients with BP <140/90 at 12 months. The primary patient reported outcome is change from baseline in self-reported patient activation, measured by the Patient Activation Measure (PAM-13), at 12 months.

Secondary outcomes

The most important secondary clinical outcome is change from baseline in systolic BP at 12 months. Additional secondary clinical outcomes include: 1) change from baseline in diastolic BP at 12 months; 2) percent with BP <130/80 mm Hg and with BP <120/80 mm Hg at 12 months; 4) change from baseline in 10-year projected probability of a CVD event (global Framingham Risk Score) at 12 months; 5) mean change from baseline in total cholesterol, low-density lipoprotein cholesterol (LDL-C), and high-density lipoprotein (HDL) and change from baseline in the percent with controlled total cholesterol, LDL, and HDL at 12 months for all patients and for the subgroup with hyperlipidemia; and 6) mean change from baseline in hemoglobin A1c and change from baseline in the percent with hemoglobin A1c < 7.0 at 12 months in patients with a diagnosis of diabetes.

Patient-reported secondary outcomes include: 1) attainment of self-determined goals related to self-management behaviors (e.g., medication adherence, healthy diet, physical activity, and smoking cessation);

2) medication adherence; 3) health related quality of life; 4) depressive symptoms; 5) patient assessment of care for chronic conditions; 6) patient ratings of trust in their care teams; and 7) hypertension knowledge and attitudes. We will compare change from baseline to 12 months to determine the effect of the intervention.

Secondary endpoint and outcomes

We will assess the following outcomes after 24 month follow-up is completed to determine the durability or “late” intervention effect: 1) the percent of patients with BP <140/90 at 24 months; 2) change from baseline in self-reported patient activation, measured by the Patient Activation Measure (PAM-13), at 24 months; 3) change from baseline in systolic and diastolic BP at 24 months. We will also compare the change from 12 months to 24 months.

Table 14 lists study measures, data sources, and collection time points.

Statistical analysis plan

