We will use mixed-effects regression models for continuous outcomes and Generalized Estimating Equations (GEE) analysis for dichotomous outcomes. For mixed-effects regression modeling, we will assume an unstructured correlation structure for longitudinal analyses of outcomes with repeated measurements over time, employ random effects to address clustering by practices, include appropriate covariate adjustment in the fixed effects, and use robust estimates for statistical inferences. The GEE approach is robust to outcome correlation misspecification, so we will just assume an exchangeable correlation structure for the outcomes, include appropriate covariates in the mean model, and use robust estimates for statistical inferences. We will use mixed-effects regression models under the MAR assumption as the basis to conduct multiple imputation for missing BP data or other outcomes as appropriate. In sensitivity analyses evaluating potential impacts under sensible informative missing

(NMAR) scenarios, we will preserve the mixed-effects regression based variance-covariance estimates, and manipulate the mean model under each informative missing scenario to carry out multiple imputation. Missing binary outcomes (e.g., controlled BP or lipids) will be derived based on multiple-imputed continuous values using appropriate observed data likelihood models as described.

Statistical analysis plan for primary outcomes

For the primary clinical outcome of BP control at 12 months we will model the binary variable BP controlled (yes/no) at 12 months using GEE with a logit link on the intervention arm indicator (CC/Stepped Care arm vs. SCP arm). Additional covariates will be included as appropriate as described previously, including appropriate cluster level characteristics and variables associated with occurrence of missing data. With correctly specified mean model, the GEE is robust to misspecification of correlation structure so the statistical inferences will account for outcome correlation due to patients clustering within practice and be valid under MCAR. The regression coefficient for the intervention arm indicator estimates the log-odds ratio of BP control at 12 months for the CC/Stepped Care arm to the SCP arm. Multiple imputation of missing BP outcomes will be carried out to impute the missing BP control outcomes to produce proper inferences under MAR and to conduct sensitive analyses under NMAR scenarios.

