For the important clinical outcome of BP control we will model the binary variable BP controlled (yes/no) at 12 and 24 months together using GEE with a logit link, and with the intervention arm indicator (CC/Stepped Care arm vs. SCP arm), the follow-up visit indicator (24 months vs. 12 months), and the interaction term of these two binary indicators as the main predictors for the mean model. Additional covariates will be included as appropriate as described previously. Multiple imputation of missing BP outcomes will be carried out to impute the missing BP control outcomes to produce proper inferences under MAR and to conduct sensitive analyses under NMAR scenarios.

For the durability outcomes of change in blood pressure and Patient Activation at 24 months, we will derive the statistical inference from mixed-effects models utilizing all outcome measures available from the 3 study time points. The regression coefficients of the arm by 24-month visit cross-product interaction term from the corresponding models estimate the difference in change in systolic BP as well as the difference in change in PAM-13 at 24 months from baseline between the intervention and the control arm, respectively. Estimates contrasting the 24 months change to the 12 months change from the modeling results will allow us to assess the durability or late effect of the intervention.

Subgroup Analyses

Patients, clinics, and health systems will be keen to know if the interventions have differential effects on different subpopulations. The pre-specified subgroup analyses include analyses by race and ethnicity. Specifically, we will compare outcomes among non-Hispanic African Americans and Hispanics to non-Hispanic whites. The analysis plan for testing heterogeneity of treatment effects is that using the full dataset, we will compare each disadvantaged subgroup (and the combined disadvantaged groups) to the presumed-advantaged group. We will test interactions of these with the intervention effect. We targeted enrolling approximately 21 patients in each race/ethnicity category per clinic to maximize power; however, these analyses will be exploratory and are not powered to detect specific differences among the subgroups.

Exploratory analysis will also be conducted to test for differential intervention effects across clinics. For this analysis clinic-indicator dummy variables and their interaction with intervention arm will be included in the GEE and mixed effects models.

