For the CC/Stepped Care arm, exploratory analysis will be conducted to determine which parts of the intervention, e.g., number of CM and CHW contacts, were more successful in improving BP control and reducing systolic BP, or if there was an overall “dose” effect.

Power calculation

We aim to recruit a total of $n=1,890$ unique patients. We planned for 20% random attrition which would yield an analytic sample of 1,500 (effective size of 50 patients per practice).^{104,105} A review of cluster-randomized trials in primary care found a median intracluster correlation coefficient (ICC) of 0.04, with an interquartile range of -0.02 to 0.21.¹⁶⁴ Assuming a 5% ICC, 15 clusters of 50 patients per intervention arm and a two-sided alpha of 0.05, we will have 80% power to detect a difference in proportion of patients with BP controlled of 11-13% (depending on whether the proportion controlled in the SCP arm is 50%-70%). With the same assumptions and sample size, using a two-sample t-test, we will be able to detect an effect size of 0.278. Operationalizing this for the primary and important secondary outcomes, we anticipate that for PAM-13, estimating a $SD=10.0$,¹⁶⁵ we would be able to detect a mean difference of 2.78 between the CC/Stepped Care and SCP arms; for systolic BP, estimating a $SD=19.5$ mm Hg,¹⁵³ we could detect a mean difference of 5.42 mm Hg between the CC/Stepped Care and SCP arms.

Design Considerations:

Participants will be considered to be enrolled at the time they are given their randomization assignment, which will occur at the end of the baseline interview. Data from all enrolled participants will be analyzed as intent-to-treat.

Missing Data

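### Table 1 claims adequate power for subgroup analyses that the SAP calls exploratory and unpowered; no outcome measures the racial/ethnic gap, and the planned BP-control interaction is on the odds-ratio scale

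*Combined protocol and SAP*

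**What the plan says.** - **Power claim.** The Outcome row of Table 1 (Section 1C) states: "We are recruiting a large sample with adequate power for subgroup analyses".
- **SAP status of those analyses.** Section 8, Subgroup Analyses, pre-specifies comparisons of non-Hispanic African American and Hispanic patients, separately and combined, with non-Hispanic White patients. On method it says "We will test interactions of these with the intervention effect". On power it says "these analyses will be exploratory and are not powered to detect specific differences among the subgroups".
- **What was powered.** Section 8, Power calculation, covers the overall arm contrast only. "Assuming a 5% ICC, 15 clusters of 50 patients per intervention arm and a two-sided alpha of 0.05", it says "we will have 80% power to detect a difference in proportion of patients with BP controlled of 11-13" percent.
- **Aim.** UH3 Specific Aim 1 (Section 2B) is "to reduce disparities in HTN and improve patient-centered outcomes". The human-subjects section repeats the disparity question under Importance of Knowledge to be Gained, there in terms of BP control rates, and under Inclusion of Women and Minorities.
- **Outcomes.** "The primary clinical outcome of the RICH LIFE Project is the percent of patients with BP <140/90 at 12 months". The other primary outcome and every secondary outcome (Sections 3D, 3E and 8A) are also levels or changes in all patients, or in patients with diabetes or hyperlipidemia. None is a difference between race groups.
- **Model.** BP control is analysed "using GEE with a logit link on the intervention arm indicator", and the coefficient is described as a log-odds ratio.

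**The concern.** The document makes two opposite statements about subgroup power, and a reader who relies on Table 1 will over-interpret the race and ethnicity results in either direction.

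The disparity question also has no matching estimand. The overall arm effect cannot answer it, because both groups can improve while the gap stays the same or widens. The interaction test does address differential effect. For BP control, however, adding arm-by-race terms to a logit model gives a ratio of odds ratios, whereas the stated question is about control rates. The two can disagree. A null interaction could be read as no change in the disparity when the gap in rates did change, and the reverse can also happen.

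**Working it through.** **Inputs from the plan.** 1,500 analysed, 15 practices of 50 per arm, ICC 0.05, two-sided alpha 0.05, 80% power, SCP control rate 50% to 70% (Section 8, Power calculation).

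**Assumptions, with their basis.** Equal thirds (the target of 21 per group per clinic); 60% combined minority against 40% White (the minimum minority share under Inclusion of Women and Minorities); Hispanic at 10% (the possible ceiling in Section 5D) against White at 40% to 45%. Each race is split equally between arms, and the control rate p is the same in all cells.

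**1. Reproduce the plan's figure.** Design effect 1 + 49 × 0.05 = 3.45; effective n per arm 750/3.45 = 217.4. Solving d = 2.80 × √{[p(1−p) + (p+d)(1−p−d)]/217.4} gives 13.2, 12.6 and 11.4 points at p = 50%, 60% and 70%, matching the stated 11 to 13. A t-test with 28 df gives a detectable effect size of 0.278, also as stated.

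**2. Between-arm difference in the gap.** With n_A and n_B patients in the two race groups over both arms:
- Variance = p(1−p)·v.
- Practice effect shared by both races, races evenly mixed (it cancels): v = 0.95 × (4/n_A + 4/n_B).
- Practice effects independent by race: v = D_A·4/n_A + D_B·4/n_B, with D = 1 + (n/30 − 1) × 0.05.
- Detectable difference = 2.80 × SE; power for 12 points = Φ(0.12/SE − 1.96).

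Worked case, 500 vs 500, shared, p = 0.5: v = 0.95 × 0.016 = 0.0152; SE = √(0.25 × 0.0152) = 0.0616; detectable 2.80 × 0.0616 = 17.3 points; power Φ(−0.01) = 50%.

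| Groups compared | Shared: detectable (points) | Shared: power for 12 | Independent: detectable (points) | Independent: power for 12 |
|---|---|---|---|---|
| 500 vs 500 (thirds) | 15.8–17.3 | 50–57% | 21.7–23.7 | 30–34% |
| 900 vs 600 (60/40) | 13.2–14.4 | 65–72% | 19.8–21.7 | 34–40% |
| 150 vs 600–675 (Hispanic 10%) | 22.6–24.9 | 27–32% | 27.0–29.7 | 20–24% |

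Ranges run over p = 0.5 to 0.7. Design effects in the independent case are 1.783 each; 2.45 and 1.95; 1.2 and 1.95–2.075.

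**3. Uneven mixing of races across practices** (expected in Section 5D), by generalised least squares with a shared practice effect:
- Practices of 50 split 40/5/5 with the majority group rotating: 19.7–21.5 points, power 35–40%.
- Six practices with 20 Hispanic patients and the other 24 with one each: 25.2–27.5 points for Hispanic vs White, power 23–27%.
- Complete segregation with 500 vs 500, an extreme (D = 3.45): 30–33 points.
- Section 5D also warns of Hispanic imbalance between arms. A 100/50 split instead of 75/75 gives 23.7–25.9 points (shared) or 28.2–30.8 (independent).

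**4. Scale.** Take SCP control of 70% in White and 50% in minority patients, with an odds ratio of 1.6 in both. White: odds (0.7/0.3) × 1.6 = 3.73, or 78.9%. Minority: odds 1 × 1.6, or 61.5%. The interaction is exactly null, but the gap is 20.0 points in SCP and 17.3 in CC/Stepped Care. Conversely, adding 12 points to both groups leaves the gap unchanged, yet the odds ratios differ (1.95 and 1.63).

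**The case against.** - **Table 1 is background and Section 8 governs.** True: someone working only from the SAP is not misled. But the sentence is current protocol text claiming a property the design lacks, and it can be quoted.
- **The formal UH3 hypothesis is overall effectiveness, and the outcomes match it.** Also true, and the primary analysis needs no change. Nothing in the plan says an overall effect will be reported as a narrowed gap, so that part of the fix is only a safeguard.
- **Subgroup analyses could mean arm effects within a race group.** These do not rescue the claim. With 500 patients in a group, effective n per arm is 250/[1 + (250/15 − 1) × 0.05] = 140, and the detectable systolic BP difference is 2.80 × 19.5 × √(2/140.2) = 6.5 mm Hg. The same formula gives 5.7 for 900 patients and 9.8 for 150, against 5.42 overall. For BP control, 500 patients give 14 to 16 points and 150 give 20 to 24.
- **The scale point is an inference and covers only BP control.** Fair. The subgroup paragraph names no scale; the odds ratio follows from the logit model. For systolic BP and PAM-13 the linear mixed models already put the interaction on the difference scale. That paragraph also promises to compare outcomes across race groups, so the interaction is not strictly the only mention, but it defines no gap measure.
- **The power figures depend on the assumed cells.** They do. With 60/40 allocation, shared effects, White patients going from 70% to 82% and minority patients from 70% to 94%, power is 81–83%, falling to about 50% with independent effects. The check in step 1 uses each arm's own rate in the variance. The common-rate formula of step 2 would give 13.4, 13.2 and 12.3 for the main effect, so step 1 confirms the inputs rather than that formula.

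**Conclusion.** The concern holds. Table 1 contradicts Section 8, and the calculation agrees with Section 8. Under the common-rate assumptions no race or ethnicity contrast reaches 80% power for a 12-point difference in the gap; the best case is 72% and the worst of the main scenarios 20%. The race mixes, the equal cell rates and the two practice-effect models are assumptions. Only the high-control case noted above passes 80%, and only with shared practice effects.

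The disparity question in Aim 1 has no outcome of its own. For BP control the one planned test is on a scale that can miss, or suggest, a change in the gap in control rates. This should be corrected; it does not threaten the primary analysis.

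**What to change.** 1. **Correct Table 1**, for example: *The sample was sized for the overall comparison of arms; analyses by race and ethnicity are exploratory and not powered.* If power figures are given, show both practice-effect assumptions and the assumed race mix.
2. **Add gap contrasts for BP control** beside the planned interaction test: the between-arm difference in the 12-month White-minus-Black, White-minus-Hispanic and White-minus-combined-minority gap, as risk differences with 95% confidence intervals, standardised from the arm-by-race GEE. Label them exploratory and unadjusted for multiplicity, and post hoc if added once data are in. State how to read them: Table 3 requires systolic BP of at least 140 mm Hg, and Section 5E makes that reading the baseline, so no participant is controlled at entry. The contrasts therefore measure differential response among patients uncontrolled at entry, not change in a population disparity.
3. **State that an overall arm effect alone will not be reported as a reduction in disparities.**

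The cost is one sentence in Table 1, short SAP wording and three contrasts from a model and data already planned. The downsides are a less favourable power statement, slightly more analysis and probably a post hoc label, since the National Death Index text in Section 7C suggests follow-up was well advanced.
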